9.5.2 Visit 2: Day 1 (Baseline and Randomization / 1st Treatment start)

1. **Inclusion/Exclusion Criteria:** Patients will be questioned to ensure they continue to meet all inclusion/exclusion criteria for the study. Patients with a negative result for the fungal culture test on Visit 1 will receive appointment cancellations for Visit 2, and will not participate in the study.
2. **Concomitant Medications:** Review and record since Visit 1.
3. **Urine Pregnancy Test:** For women of childbearing potential, a urine pregnancy test will be performed to evaluate pregnancy. Any patient with a positive pregnancy test will not be allowed to participate in the study.
4. Trimming target nail, if needed.
5. **Investigator Clinical Assessment:** Perform a foot/toenail exam. Infected toenail count will be recorded. Nail appearance will be recorded.
6. **Evaluation of Toenail Appearance and Condition:** The investigator and patients will perform a visual assessment and rate target toenail appearance and condition per Appendix A.
7. **Visual Assessment:** The target toenail involvement will be recorded. The toenail (one of the two great toenails) that meets inclusion/exclusion criteria will be identified and designated as the target toenail and used for all further evaluations.
8. **Planimetry Assessment:** Appropriate photographic documentation will be obtained in accordance with Canfield Scientific Inc. guidelines for the planimetry assessment.
9. **Dispense Randomized Study Product and Administration Instructions:** Patients will be randomly assigned to one of the three **treatment groups** of the study, and will receive a randomization number. Qualified patients will be provided with two bottles of randomized study product. A set of instructions to apply the study product at home will be provided, along with supplies including standardized non-medicated bar of soap and towel.
10. **Dispense Patient Diary:** A diary along with instructions to record dose frequency and timing, adverse events and concomitant medications will be provided.
11. **Administer First Dose:** Clinic staff member will observe the first application of study product by the patient in the clinic.

A Randomized, Placebo-Controlled, Double-Blind, Parallel-Group, Multi-Site Phase 2b Clinical Study to Assess the Efficacy, Safety and Tolerability of 8-Week Regimens of Novexatin®, 10% Topical Solution (Taro Pharmaceuticals, USA, Inc.) in Patients with Mild to Moderate Onychomycosis

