9.6.13 Visual Assessment and Planimetry

At screening, both big toenails can be evaluated for nail involvement if the subject has a bilateral infection of the big toenails. At Visit 2, the target toenail will be identified and nail involvement of the target toenail over time will be monitored visually by an investigator at every visit. If the nail involvement does not reach zero at the final visit, the investigator will visually assess the nail involvement based on the following range:

- 0%
- > 0-5%
- 6-9%
- 10-35%
- > 35%

At Visit 2 and all subsequent visits, the target toenail will also be monitored by planimetry. Appropriate photographic documentation of the target toenail will be obtained for the planimetry assessment at Visit 2 and submitted to Canfield Scientific, Inc. to determine the nail involvement. At all subsequent visits, appropriate photographic documentation of the same target toenail will be obtained and submitted to Canfield Scientific, Inc. to determine the nail involvement. Photographs of the target toenail will be collected using the procedures provided by Canfield Scientific, Inc. The photographs from each visit will be processed and reviewed by an independent panel. An image analysis will be conducted and numerical values for the % affected (in terms of surface affected for both the healthy and pathologic area of the target nail) will be reported. The % affected will be used to judge Satisfactory Clinical Cure.

9.6.14 Investigator Clinical Assessment:

An investigator will perform an exam of foot/toenail at each visit. Infected toenails will be counted and recorded. Nail appearance will be recorded.

9.6.15 Evaluation of Toenail Condition/Appearance:

The toenail, one of the two great toenails, that the investigator considers to be the most appropriate as the target toenail will be identified and designated as the "target toenail" at Visit 2 and used for evaluations.

The overall appearance of the target toenail over time will be monitored during the study:

1. Self-assessed by patients. The results of the self-assessment will be recorded by the patient before beginning therapy at Visit 2 and at all subsequent visits. Patients will use a 5-point scale (see Appendix A) for target toenail appearance.

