### **Secondary Endpoints:**

1. The proportion of patients in each treatment group with a complete or almost complete therapeutic cure of onychomycosis of the target toenail assessed at each of the two test-of-cure visits (Day 141 and Day 365).
2. The proportion of patients in each treatment group with a mycological cure of the target toenail assessed at each of the two test-of-cure visits (Day 141 and Day 365).
3. The proportion of patients in each treatment group with a complete clinical cure of the target toenail assessed at each of three test-of-cure visits (Day 141, Day 281 and Day 365).
4. The proportion of patients in each treatment group with a satisfactory clinical cure of the target toenail assessed at each of three test-of-cure visits (Day 141, Day 281 and Day 365).

**Complete therapeutic cure** is defined as both complete clinical and mycological cure of the target toenail

**Almost complete therapeutic cure** is defined as both mycological and satisfactory clinical cure of the target toenail

**Mycological cure** is defined as a negative KOH test **and** a negative fungal culture.

**Complete clinical cure** is defined as 0% nail involvement.

**Satisfactory clinical cure** is defined as  $\leq 5\%$  of the target toenail involvement.

**NOVUM PHARMACEUTICAL RESEARCH SERVICES  
STATISTICAL ANALYSIS PLAN**

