**Novexatin 10% topical solution**

**Protocol / Study No. NVXT 1404/71442603**

**8.1.2 Demographic and Other Baseline Characteristics**

Baseline comparability of all treatment groups will be evaluated separately in the ITT and Safety populations.

The following baseline demographics (determined from their initial study visit) will be evaluated:

- Age (years)
- Gender (male/female)
- Ethnicity (Hispanic/non-Hispanic)
- Race (White, Black/African American, Native Hawaiian or Other Pacific Islander, Asian, American Indian or Alaska Native, Other)

Summary tables by treatment group will be presented. Continuous variables will be summarized using descriptive statistics (n, mean, standard deviation, median, minimum, maximum).

Categorical variables will be summarized using frequencies and percentage.

Baseline comparability of the treatments will be presented using Chi-square test for the categorical variables, and Analysis of Variance for the continuous variables.

All data will be listed by treatment group and patient.

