**NOVUM PHARMACEUTICAL RESEARCH SERVICES**  
**STATISTICAL ANALYSIS PLAN**

**Novexatin 10% topical solution**

**Protocol / Study No. NVXT 1404/71442603**

the 8-week treatment regimens in Groups A, B and C.

Descriptive statistics will be summarized for the primary and secondary endpoints (including planimetry data) by study group. As this is a multi-centered study, results may also be presented by study site.

In order to preserve an overall type-I error (alpha) of 5% for evaluation of complete and almost complete therapeutic cure, complete and satisfactory clinical cure and mycologic cure, a hierarchical evaluation scheme will be employed for the primary and secondary endpoints. The four comparisons of interest for the primary endpoint and the secondary endpoints -1 and -2 are:

1. Group B versus Group C – at the test-of-cure visit at Day 365
2. Group A versus Group C – at the test-of-cure visit at Day 365
3. Group B versus Group A – at the test-of-cure visit at Day 365
4. (Group A + Group B) versus Group C – at the test-of-cure visit at day 141

The five comparisons of interest for the secondary endpoints -3 and -4 are:

1. Group B versus Group C – at the test-of-cure visit at Day 365
2. Group A versus Group C – at the test-of-cure visit at Day 365
3. Group B versus Group A – at the test-of-cure visit at Day 365
4. (Group A + Group B) versus Group C – at the test-of-cure visit at Day 281
5. (Group A + Group B) versus Group C – at the test-of-cure visit at Day 141

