Statistical testing will begin with comparison 1. If statistical significance is attained with comparison 1 ( $p < 0.05$ ), then a claim of superiority for comparison 1 can be made and the next comparison in the hierarchical evaluation scheme can be tested for statistical significance. If statistical significance is not attained for comparison 1 ( $p \geq 0.05$ ), then testing of all subsequent comparisons is stopped. The hierarchical, conditional-stepwise evaluation scheme allows for each comparison to be evaluated at the 5% level, while preserving an overall type I error rate of no more than 5%. For the proportion of patients in each treatment group with a complete and almost complete therapeutic cure, complete and satisfactory clinical cure and mycological cure of onychomycosis of the target toenail, the statistical analysis for superiority will be conducted using a two-sided Cochran-Mantel-Haenszel (CMH) exact test, stratified by clinical site, at the 5% significance level. The primary and secondary analyses will be performed using an observed case (OC) analysis in the ITT population. Patients discontinued because of lack of treatment effect will be included in the primary analysis as treatment failures.

The following two sensitivity analyses will also be performed on the primary efficacy endpoint in the hierarchical, conditional-stepwise evaluation scheme:

**NOVUM PHARMACEUTICAL RESEARCH SERVICES  
STATISTICAL ANALYSIS PLAN**

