**8.7 Changes to the Protocol Defined Statistical Analysis Plan**

The protocol states that the statistical analysis for superiority will be conducted using two-sided Z-Tests and a pooled response rate for the standard error of the difference in proportions for each comparison of interest. The CMH exact test stratified by clinical site is preferred for a multi-site study for which the randomization is intended to be balanced among treatments within each site (i.e., stratified by site), because it accounts for the variability in clinical site whereas the Z-test does not account for site variability in the model. During the analysis, the statistical analysis for superiority will be conducted using a two-sided Cochran-Mantel-Haenszel (CMH) exact test, stratified by clinical site, at the 5% significance level.

The wording in section 8.5 “Methods for Handling Missing Data” was updated to coincide with the ITT definition. The ITT states that patients will be included in the ITT as long as they have received one dose of assigned study product and had a positive mycological culture at Visit 1.

Additional analyses that were not delineated in the protocol were included in section 8.2.3 of the SAP.

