**L16.2.6.2.1 Listing of Investigator Visual Assessment (Percent Nail Involvement of the Target Toenail)**

| Treatment Group   | Patient Randomization Number | Visit1 | Visit2 | Visit3 | Visit4 | Visit5 | Visit6 | Visit7 |
|-------------------|------------------------------|--------|--------|--------|--------|--------|--------|--------|
| Treatment Group A | xx-xxxx                      | xxx    |

Treatment Group B  
Treatment Group C

---

Treatment Group A: Novexatin® 10% Topical Solution for Days 1 – 56 and Placebo (Vehicle) Topical Solution for Days 281 – 336

Treatment Group B: Novexatin® 10% Topical Solution for Days 1 – 56 and Days 281 – 336

Treatment Group C: Placebo (Vehicle) Topical Solution for Days 1 – 56 and Days 281 – 336

Created on: ddmmmyy hh:mm

Page 1 of N

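### The primary cure test adjusts for site only: Visit 2 nail involvement is collected but is neither adjusted for nor tabulated by arm

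*SAP*

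**What the plan says.** - **Primary test.** SAP 8.2.1: "the statistical analysis for superiority will be conducted using a two-sided Cochran-Mantel-Haenszel (CMH) exact test, stratified by clinical site". SAP 8.7 prefers this to the protocol's pooled Z test "because it accounts for the variability in clinical site whereas the Z-test does not account for site variability in the model". Under SAP 8.2.2, if no treatment-by-site interaction is found, nothing further is adjusted for.
- **Other efficacy analyses.** The two sensitivity analyses change only the handling of missing outcomes. SAP 8.2.3 uses planimetry to redefine cure and to select patients within 10-35% involvement. It does not use it as a covariate.
- **Baseline data collected.** Protocol 9.5.2 (Visit 2, steps before the first application): "The target toenail involvement will be recorded". Protocol 9.6.13 adds: "Appropriate photographic documentation of the target toenail will be obtained for the planimetry assessment at Visit 2". The clinical half of the primary endpoint is on this scale: complete clinical cure "is defined as 0% nail involvement" (SAP 6).
- **Baseline data tabulated.** SAP 8.1.2: "The following baseline demographics (determined from their initial study visit) will be evaluated". The list that follows is age, gender, ethnicity and race, and shells T14.1.2.1 and T14.1.2.2 match it. Percent involvement appears only in patient listings: L16.2.6.2.1, "Listing of Investigator Visual Assessment (Percent Nail Involvement of the Target Toenail", and its planimetry counterpart L16.2.6.2.2.
- **A general promise.** SAP 8.2.1: "Descriptive statistics will be summarized for the primary and secondary endpoints (including planimetry data) by study group". No shell shows percent involvement by arm at baseline.

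**The concern.** The SAP changed the primary test so that it would account for a source of outcome variation, namely site. The same reasoning applies to the starting value of the scale on which clinical cure is judged, but the plan does not use it. Randomisation is in blocks of 3 within site with no severity stratum (Protocol 9.4.3.2), so involvement is balanced across arms only by chance. The primary analysis is observed-case with 23% drop-out allowed for, so the analysed set may be less balanced than the randomised one.

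If involvement predicts cure, the unadjusted analysis is less precise than it could be, and an imbalance passes straight into the reported difference. Table V shows crude proportions and a crude difference, with no confidence interval or adjusted estimate. Protocol 10.6 says the efficacy results will size Phase 3. No planned table of percent involvement would alert a reader to such an imbalance.

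**Working it through.** **1. The plan's own figure.** Inputs from Protocol 10.2 and SAP 5: 49% vs 21%, two-sided 0.05, pooled Z test, 46 per arm, 23% drop-out.

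- Pooled rate: (0.49 + 0.21)/2 = 0.35. Null SE: sqrt(2 × 0.35 × 0.65/46) = 0.0995.
- Alternative SE: sqrt((0.49 × 0.51 + 0.21 × 0.79)/46) = 0.0951.
- Power: Φ((0.28 − 1.96 × 0.0995)/0.0951) = 81.5%.
- Enrolment: 46/0.77 = 59.7, so 60 per arm and 180 in all.

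The stated design reproduces.

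**2. Assumptions not in the documents.** These are prognostic strength (odds ratio, OR, for complete cure per SD of involvement, 1 to 3); involvement uniform on the 10-35% entry window, SD 25/sqrt(12) = 7.2 points; 8 or 15 sites; and site log-odds SD 0.3.

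**3. Power.** Simulation used 6,000 trials per setting, with 60 per arm placed in sites and 46 per arm kept. Intercepts were solved so that marginal cure is 49% and 21%. Monte Carlo SE is about 0.5 points. The adjusted test is a site-stratified CMH on residuals from a treatment-blind logistic regression of cure on involvement.

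| OR per SD | Sites | Exact CMH (planned) | Large-sample CMH | Adjusted CMH | Adjusted − large-sample |
|---|---|---|---|---|---|
| 1 | 8 | 78.2 | 81.4 | 80.8 | −0.6 |
| 1 | 15 | 77.9 | 80.9 | 80.4 | −0.5 |
| 1.5 | 8 | 77.3 | 80.7 | 81.7 | +1.0 |
| 1.5 | 15 | 77.8 | 81.0 | 81.4 | +0.4 |
| 2 | 8 | 79.0 | 82.1 | 85.2 | +3.1 |
| 2 | 15 | 78.1 | 81.3 | 84.2 | +2.9 |
| 3 | 8 | 78.7 | 81.8 | 88.7 | +6.9 |
| 3 | 15 | 76.4 | 79.9 | 87.4 | +7.5 |

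The fair comparison is the last two tests. The exact test's further 3 points or so are the price of exactness, not of omitting the covariate.

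A separate simulation used logistic adjustment, 10 equal sites and no site effect (3,000 runs). Site CMH vs adjusted power was 80.6 vs 80.7, 80.7 vs 81.9, 82.3 vs 84.6 and 82.1 vs 89.5 at OR 1, 1.5, 2 and 3. The pattern is the same.

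**4. Type I error.** With both rates at 35%, rejection was 3.5-4.4% (exact), 4.6-5.3% (large-sample) and 4.7-5.4% (adjusted); Monte Carlo SE about 0.3 points. The planned test is valid, and adjustment does not inflate error beyond simulation noise.

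**5. Chance imbalance.** The 95% limit on the difference in mean involvement is 1.96 × 7.217 × sqrt(2/46) = 2.95 points. Regressing the unadjusted cure difference on the imbalance gives the shift at that limit: 3.1-3.3 points (OR 1.5), 5.0-5.7 (OR 2) and 7.5-7.7 (OR 3), against a planned 28. In the separate simulation the standardised, involvement-adjusted estimate moved by at most 0.2 points at these odds ratios.

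**6. Precision of the estimate.** SD of the risk difference, unadjusted vs standardised (logistic model with treatment and involvement, no site terms), was 9.4 vs 9.0-9.1 points at OR 2 and 9.5 vs 8.6-8.7 at OR 3.

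**7. Dilution by the mycological half.** Suppose 70% of clinically cured patients are also mycologically cured, whatever their involvement. Clinical cure is then 0.49/0.70 = 70% (active) and 0.21/0.70 = 30% (placebo). A clinical-cure OR of 3 per SD becomes, as the best-fitting logistic slope for complete cure, 1.8 (active) and 2.6 (placebo). At 90% it becomes 2.6 and 2.9.

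**The case against.** The strongest reply is that nothing is wrong with the test. A site-stratified CMH matches randomisation within site, and adding a covariate that played no part in randomisation is an efficiency preference. The benefit rests on a prognostic strength the documents do not give, and the upper range is steep. The 10-35% window spans 25/7.217 = 3.46 SD, so OR 3 per SD means 3^3.46, about a 45-fold difference in cure odds across an already narrow window; OR 2 means about 11-fold and OR 1.5 about 4-fold. At OR 1.5 or below the power gain is about 1 point or less. All of this stands, and it is why the point is conditional and shown as a range.

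The imbalance shift is also not a hazard on top of sampling error. It is already inside the 9.4-point SD. At OR 2 a 95% half-width goes from 1.96 × 9.4 = 18.4 to about 17.6-17.8 points. That stands too. Adjustment removes an identifiable part of the error; it does not cure a bias.

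The precision figures in step 6 leave out site terms, although the recommended model has them. With 8 or 15 equal unpooled sites (1,500 runs), the unadjusted SD vs the SD with site terms was 9.45 vs 9.49 and 9.38 vs 9.40 at OR 1.5 (no gain), 9.62 vs 9.34 and 9.41 vs 9.21 at OR 2, and 9.48 vs 8.58 and 9.44 vs 8.79 at OR 3. A further check found that site terms change the SD by 0.1 point or less, so the conclusion holds. With 15 unpooled sites, however, about 75% of trials had a site with all or no cures. The pooling in SAP 8.2.2 therefore has to be settled first.

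Last, T14.3.10 does show a Visit 2 appearance rating by arm, and SAP 9 says the shells may not be complete. The rating is a 5-point score, not percent involvement, and SAP 8.1.2 names no disease characteristic. The gap is softened, not closed.

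**Conclusion.** The concern holds. Site is the only adjustment in the primary test, Visit 2 involvement is collected but unused in it, and no table shell summarises it by arm. This is a matter of efficiency and robustness, not of validity.

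Its size depends on an unknown. Adjustment loses about half a power point if involvement is not prognostic, gains about 1 point or less at OR 1.5 per SD, about 3 at OR 2 and about 7 at OR 3. The mycological component makes the upper end less likely. The gains also rest on the assumed uniform 10-35% spread and the assumed number and variability of sites. The change should be made because the data are already scheduled and the loss is small if involvement proves unimportant. The missing baseline summary should be added whatever the prognostic strength.

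**What to change.** Before unblinding, amend SAP 8.2.1 and record the change in SAP 8.7:

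1. Prespecify a site-stratified analysis of complete therapeutic cure adjusted for continuous Visit 2 involvement: a CMH mean-score test, stratified by site, on residuals from a treatment-blind logistic regression of cure on involvement. Do not split the site strata further by baseline, since they would become sparse. Make this primary or, if the exact CMH stays primary, a named supportive analysis. In the second case the primary test itself gains no power.
2. Report a standardised risk difference with 95% CI from a separate unconditional logistic model with treatment, involvement and pooled-site terms.
3. Name one covariate per endpoint: the investigator's Visit 2 value for the investigator-based endpoint and Visit 2 planimetry for the SAP 8.2.3 endpoint. Replace a missing value by the mean over all arms.
4. Add Visit 2 percent involvement, by investigator and by planimetry, by arm to T14.1.2.1 and T14.1.2.2.

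The cost is SAP wording, two table rows and a few lines of code, with no new data or visits. The downside is that the adjusted result is model-based and large-sample rather than exact, and costs about half a power point if involvement does not predict cure.

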10.2 Determination of Sample Size

The primary statistical analysis of interest is a comparison of the rates of therapeutic cure (as defined by "clinical cure" AND "mycological cure") of Novexatin® 10% topical solution to the rate of therapeutic cure of placebo in the Intent-to-Treat Population (ITT). The rate of therapeutic cure for the Novexatin® 10% topical solution 8-week regimens is expected to be approximately 49%. The rate of therapeutic cure for placebo is expected to be approximately 21%. Approximately 46 patients in each treatment group in the ITT population will provide over 80% power to show a difference at $p < 0.05$ (two-sided Z test and a pooled response rate for the standard error of the difference in proportions) between each of the active treatment groups and the placebo group. To allow for a 23% drop-out rate, a total of 180 patients will be enrolled in the study, with up to 60 patients in each of the treatment groups.

A Randomized, Placebo-Controlled, Double-Blind, Parallel-Group, Multi-Site Phase 2b Clinical Study to Assess the Efficacy, Safety and Tolerability of 8-Week Regimens of Novexatin®, 10% Topical Solution (Taro Pharmaceuticals, USA, Inc.) in Patients with Mild to Moderate Onychomycosis

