**Novexatin 10% topical solution**

**Protocol / Study No. NVXT 1404/71442603**

49%. The rate of therapeutic cure for placebo is expected to be approximately 21%. Approximately 46 patients in each treatment group in the ITT population will provide over 80% power to show a difference at  $p < 0.05$  (two-sided Z test and a pooled response rate for the standard error of the difference in proportions) between each of the active treatment groups and the placebo group. To allow for a 23% drop-out rate, a total of 180 patients will be enrolled in the study, with up to 60 patients in each of the treatment groups.

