**Novexatin 10% topical solution**

**Protocol / Study No. NVXT 1404/71442603**

**7. STUDY POPULATIONS**

**Intent-to-Treat (ITT) Population**

- All randomized patients who applied at least one dose of assigned study product
- Had a positive mycological culture screening (Visit 1)

The primary analyses will be conducted on the ITT population.

Patients who return randomized product bottles with evidence of intentional tampering or unblinding will be excluded from the ITT population and included in the Safety population.

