**8.5 Methods for Handling Missing Data**

For demographic and baseline characteristics, each variable will be analyzed using all available data. Patients with missing data will be excluded only from analyses for which data are not available.

The following rules and conventions will be used for patients who terminate from the study early or are dropped from the study because of protocol deviations.

Any patient who either requests to be dropped from the study because of lack of therapeutic efficacy or is dropped by the Investigator for lack of therapeutic efficacy will automatically be considered a "clinical failure" regardless of their target toenail assessment score at the termination visit.

Any patient who uses any protocol restricted medication specifically for the treatment of their infection will be discontinued from further participation in the study and automatically be considered a "clinical failure" regardless of their target toenail assessment score at the last visit.

Any patient who uses any protocol restricted medication NOT specifically for the treatment of their onychomycosis will be discontinued from further participation in the study. The patient will be considered a "clinical cure" or "clinical failure" based on the target toenail assessments at the termination visit.

Any patient who is dropped for any reason other than those covered above will be included in the ITT, provided they had a positive baseline culture and applied at least one dose of the study product. Examples would include: failure to use the study products as required by the protocol, patient withdraws consent for continued participation, patient fails to make study visits on a timely basis.

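### The primary test is observed-case inside a population called ITT, so whether a patient without a test-of-cure result counts depends on the recorded reason for leaving; this can overstate cure and bias the comparison.

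*SAP*

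**What the plan says.** SAP section 7 takes into ITT "All randomized patients who applied at least one dose of assigned study product", provided the Visit 1 culture was positive. No post-baseline result is needed, and Protocol 10.3.1 agrees. SAP 8.7 records that the missing-data wording in 8.5 was changed to match this definition; Protocol 9.3.5 had asked for a post-baseline visit.

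SAP 8.2.1, like Protocol 10.6, then says: "The primary and secondary analyses will be performed using an observed case (OC) analysis in the ITT population". It adds one exception: "Patients discontinued because of lack of treatment effect will be included in the primary analysis as treatment failures". SAP 8.5 gives a second: "Any patient who uses any protocol restricted medication specifically for the treatment of their infection will be discontinued from further participation in the study". Those patients are scored as clinical failures, so they cannot be therapeutic cures. Patients who use restricted medication for some other purpose are classed from the nail assessment at termination. Patients who withdraw consent or miss visits stay in ITT, but if they have no test-of-cure result nothing brings them into the primary test.

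For the primary endpoint, 8.2.1 plans two sensitivity analyses at Day 365, with similar ones at Day 141. Number 1 counts missing as failure in every group. Number 2 counts missing as success in Group C and failure in Groups A and B. Section 8.2.3 extends them to the versions using Canfield's evaluation. The protocol-defined secondary endpoints have none.

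On size, SAP section 5 says "Approximately 46 patients in each treatment group in the ITT population will provide over 80% power to show a difference at" p < 0.05, for cure rates of 49% and 21%, and "To allow for a 23% drop-out rate, a total of 180 patients will be enrolled in the study".

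**The concern.** The named population and the analysed population differ. Two uncured patients who leave on the same day are scored differently if one form says lack of effect and the other says consent withdrawn. Over 52 weeks with a 32-week rest period, an uncured patient could plausibly be recorded either way.

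Three things are at stake. The superiority claim in the testing hierarchy rests on the observed-case p-value. Neither document says what follows if a sensitivity analysis disagrees with it. And Protocol 10.6 says that the efficacy results will be used to size Phase 3.

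**Working it through.** **1. The plan's own figure.** Inputs from SAP section 5 and Protocol 10.2: p1 = 0.49, p2 = 0.21, two-sided 5%, pooled Z test, 23% dropout.

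n = [1.96·√(2·0.35·0.65) + 0.842·√(0.49·0.51 + 0.21·0.79)]² / 0.28² = (1.322 + 0.543)² / 0.0784 = 44.4, so 45 per group (stated: about 46).

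Power at 46 = Φ[(0.28·√46 − 1.322)/0.645] = Φ(0.895) = 81.5%. This reproduces the statement of over 80%.

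Allowance for dropout: 46/0.77 = 59.7, so 60 per group and 180 in total. Conversely 60 × 0.77 = 46.2. The 46 is therefore the expected evaluable set. The ITT set, as defined, is close to 60.

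**2. Possible overstatement.** If completers cure at rate c, a share d is missing, and the missing cure at f times the completers' rate, the rate in all patients is c·[(1 − d) + d·f]. With d = 0.23:

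| f | Active (c = 49%) | Placebo (c = 21%) | Difference |
|---|---|---|---|
| 1 | 49.0% | 21.0% | 28.0 points |
| 0.5 | 43.4% | 18.6% | 24.8 points |
| 0 | 37.7% | 16.2% | 21.6 points |

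**3. False-positive rate.** True cure is 30% in both arms, with 60 randomized per arm. The rate among those analysed is 0.30/[(1 − d) + d·f], where d is the share excluded. Rejection probabilities come from exact binomial enumeration, with the analysed n fixed at its expected value. The SAP replaced the pooled Z test with an exact CMH test stratified by site. Site sizes are not given, so Fisher's exact test stands in for it. The 30% cure rate, dropout splits and labelling patterns are assumptions; the documents give none by arm or reason.

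| Analysis and pattern (active vs placebo) | n analysed | Rates | Pooled Z | Fisher |
|---|---|---|---|---|
| Observed-case; 30% vs 15% dropout, unrelated to outcome | 42 / 51 | 30.0 / 30.0% | 5.5% | 3.8% |
| Observed-case; 30% vs 15%, dropouts cure at half the completers' rate | 42 / 51 | 35.3 / 32.4% | 6.8% | 4.5% |
| Observed-case; 30% vs 15%, all dropouts uncured | 42 / 51 | 42.9 / 35.3% | 12.4% | 8.9% |
| Observed-case; 23% in both, all uncured, half of placebo and no active dropouts labelled lack of effect | 46 / 53 | 39.0 / 33.9% | 9.2% | 6.4% |
| Missing = failure; all dropouts uncured | 60 / 60 | 30.0 / 30.0% | 5.3% | 3.1% |
| Missing = failure; 15% vs 30%, unrelated to outcome | 60 / 60 | 25.5 / 21.0% | 9.2% | 5.7% |

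In the third row, 12.0 of the 12.4 points are false wins for active. With the split reversed, false wins for active fall to 0.3% and the bias favours placebo.

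**4. Power if missing counts as failure.** At 23% missing the rates are 0.77 × 49% = 37.7% and 0.77 × 21% = 16.2%. Power at 60 per group = Φ[(0.2156·√60 − 1.96·√(2·0.2695·0.7305))/√(0.3773·0.6227 + 0.1617·0.8383)] = Φ(0.723) = 76.5%. Exact enumeration gives 77.9%, and Fisher 70.4%. Observed-case at 46 per group gives 81.5% by pooled Z and 75.6% by Fisher. By the pooled-Z formula, the missing = failure figure is 85.3% at 10% missing and 70.9% at 30%; at 23% missing, 66 per group would be needed for 80%.

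**The case against.** The strongest reply is that the plan already contains the alternative. Missing = failure is sensitivity analysis 1, with its own shell (Table VI), and a worst case against active follows in Table VII. The dispute is then which of two planned tables is called primary in a Phase 2b trial. That largely stands, and it is why the change is cheap. It does not supply a rule for discordant results. Nor does sensitivity analysis 2 settle much: at 23% missing and the planned effect it compares 37.7% with 0.77 × 21% + 23% = 39.2%, so it could not show superiority.

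It is also fair that the dropout patterns are hypothetical. The products are described as indistinguishable and the investigators as blinded (Protocol 9.4.4), and adverse-event incidence was similar to placebo in the Phase I/IIa studies (Protocol 7.4). Large differences between arms in dropout or labelling are possible, not expected.

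Not every other dropout disappears. Besides the two groups scored as failures, Protocol 9.3.5 asks for Visit 7 procedures at early termination. The documents do not say, however, whether a reading taken early at termination counts as observed at Day 365.

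Finally, missing = failure has its own bias, as the last row of the error table shows. This stands and limits what the change can claim.

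**Conclusion.** The primary analysis does not use all ITT patients, and its scoring of missing patients depends on the recorded reason. The text establishes both. The statistical consequence is conditional. Under the assumptions in the working, two-sided error reaches 12.4% (pooled Z) or 8.9% (Fisher) when outcome-related dropout differs by arm, and about 9% or 6.4% when only the labelling differs.

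A reader might infer more, and the documents do not support it:

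- That 23% of patients will be dropped. The 23% is a planning allowance with no split by arm or reason, and any lack-of-effect dropouts within it are retained.
- That cure rates are overstated as a matter of course. This needs excluded patients to cure less often than those analysed. Keeping lack-of-effect dropouts as failures lowers the observed rates.
- That unequal dropout by itself inflates the false-positive rate. If dropout is unrelated to outcome, the error is 5.5% or 3.8%.
- That the bias favours the drug. It can run either way.
- That Phase 3 will be sized on completer rates. Protocol 10.6 refers to efficacy results in general, and missing = failure rates will be available for the primary endpoint.

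**What to change.** - Make sensitivity analysis 1 the primary analysis on all ITT patients: no result at Day 365 or Day 141 means not cured, whatever the reason. Keep observed-case and sensitivity analysis 2 as supportive.
- Say whether an assessment made at early termination counts as a Day 365 result, and how a disagreement between the primary and supportive analyses will be read. If observed-case stays primary, that last statement is the minimum.
- Give the protocol-defined secondary endpoints the same missing-data rule, at least as a sensitivity analysis.
- In SAP section 5, Protocol 10.2 and the synopsis, describe 46 as the evaluable number, not the ITT number. Restate power for 60 per group under the planned exact CMH test.

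The cost is mainly SAP wording, since both primary-endpoint analyses are already specified and have shells. There are two downsides. At 23% missing, stated power falls from 81.5% to about 77–78% by pooled Z, or from about 76% to about 70% by Fisher. And the new primary analysis is itself biased if dropout unrelated to outcome differs by arm (15% active vs 30% placebo at 30% cure: 9.2% by pooled Z, 5.7% by Fisher), which is why the observed-case result should still be reported beside it.
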